3 STUDY OBJECTIVES

1. Assess if ESG achieves safety and efficacy threshold as defined by joint societal consensus statement by ASGE and ASMBS
2. Assess the impact of ESG on obesity related co-morbidities (Hypertension and Diabetes)
3. Assess the mid-term durability of weight loss achieved by ESG at 24 months.
4. Assess the impact of re-tightening the ESG on weight loss trajectory.

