4 STUDY DESIGN

4.1 General Description

This study is a multi-center, randomized, open-label clinical trial evaluating the efficacy and safety of ESG as an adjunct to life-style intervention for weight loss and improvement in obesity-related co-morbidities compared to lifestyle intervention alone in participants with a BMI ≥ 30 and ≤ 40 kg/m² who have failed to achieve and maintain weight loss with a non-surgical program.

Participants will be recruited from outpatient clinical weight loss clinics and from study-related institutional review board (IRB) approved advertisements. The cohort will include nor more than 50 patients without at least one of a) hypertension (HTN) on one or more anti-hypertensive medications or b) type II diabetes mellitus (DM) on oral agents only with HbA1c ≤ 9 . Enrollment will be tracked continuously and enrollment closed to non-DM, non-HTN patients after meeting the target for that group.

Two hundred eligible participants will be stratified into three groups (obesity, obesity-hypertension, and obesity-diabetes) and then block-randomized 1 to 1.5 to treatment (80 participants) and control (120 participants) groups alone as depicted in the diagram on page 16. All treatment group participants will undergo endoscopy and those without endoscopic contraindications will undergo the ESG. All control subjects will follow a low-calorie, healthy lifestyle intervention only for 12 months. After 12 months of lifestyle intervention, eligible control participants will crossover to receive the ESG. Those who had the ESG will undergo a repeat upper endoscopy at 52 weeks +- 4 weeks to evaluate the durability of the plications and re-tighten the ESG if needed with continued follow-up for 12 additional months.

The study will have two levels:

1. Level 1: the randomized study phase with primary outcomes for both groups evaluated at 12 months
2. Level 2: the crossover, non-randomized study phase with outcomes for a) the initial treatment group at 24 months post ESG (12 months after the re-tightening procedure) b) for the controlled cross-over group evaluated at 12 months after ESG

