4.2 Endpoints

4.2.1 Effectiveness

Primary:

- % EWL at 12 months from randomization by randomized arm measured at the week 52 visit. The null hypothesis is no difference in mean %EWL between randomized arms.

Secondary:

- Proportion with $\geq 25\%$ EWL at 12 months by randomized arm
- Change in hypertension in the ESG group compared to LS only

- Proportion of patients off or with reduction in their antihypertensive medications in the randomized control arm compared to lifestyle control at 12 months
- Change in systolic and diastolic blood pressure in the randomized arm compared to lifestyle control at 12 months
- Comparing diastolic and systolic blood pressures as continuous variables 12 months after ESG (compared to baseline) in the entire cohort that received ESG both in the randomized and cross-over segments of the trial
- Change in type II diabetes in the ESG groups compared to LS only
 - Proportion of patients off or with reduction in their diabetes medications in the randomized arm compared to lifestyle control at 12 months
 - Change in HgbA1c in the randomized arm compared to lifestyle control at 12 months
 - Comparing HgbA1c as a continues variable 12 months after ESG (compared to before) in the entire cohort that received ESG both in the randomized and cross-over segments of the trial.
- %TBWL in the ESG group compared to LS only
- % of patients in the ESG group achieving > 5% TBWL compared to LS only
- % of patients in the ESG group achieving > 10% TBWL compared to LS only
- Durability of the plication evaluated by endoscopy at 12 months (level 1) and effectiveness of re-tightening procedure performed at 12 months (level 1) in maintaining and / or enhancing weight loss at 24 months. Durability of the plication and procedure is defined as greater than 70% of the cohort undergoing repeat endoscopy achieving a score of ≥ 1 out of 3 prior to re-tightening (Grading system and evaluation in appendix). Efficacy of re-tightening is defined as $\geq 50\%$ of the cohort undergoing the re-tightening maintaining or losing weight compared to the re-tightening weight at 12 months after the re-tightening procedure.
- Incidence of esophagitis at repeat endoscopy at 12 months (level 1). (LA grading system in form in appendix)
- Changes in quality of life assessed using standard validated questionnaires (IWQOL-lite and SF-36)
- Changes in depression assessed using PHQ-9 questionnaire

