ESG patients will undergo a standard moderate intensity life-style intervention administered over 12 visits in the first year after ESG. Participants will be required to follow up with their prescribing physician to make any necessary changes to their hypertension and/or type II diabetes medications at 3, 6, 9 and 12 months. Completion of patient follow-up with providers for medication adjustment will be captured with completion of the appropriate CRF at the corresponding visits. In the event that participants are unable to contact their physician or participants are experiencing symptoms related to the medication dosing requiring urgent action, the study team will make any necessary

changes in their medication dosing and document these changes appropriately in the relevant CRFs. Any medication changes will be monitored and recorded by the study team.

All ESG patients in Level 1 (80) will be evaluated for %EWL at the end of Level 1 (measurement of primary endpoint). Those ESG patients who have achieved >25% EWL at the end of Level 1 will not undergo a repeat endoscopy and will continue to follow-up with a lifestyle intervention in Level 2. Those ESG patients who have not achieved >25% EWL at the end of Level 1 will undergo a repeat upper endoscopy at 52 to 60 weeks to assess the durability of the plications (see Plication Durability form), and perform a retightening of the ESG if needed. The need for re-tightening will be determined by the PI after evaluating the sutures based on a grading system presented in the retightening CRF. The retightening procedure will be performed if at least one of the three portions (proximal, mid, and distal) of the endoscopic sleeve is non-tubular in shape. For each tubular third of the sleeve, 1 point will be given. A score of 3/3 means the entire (proximal, mid, and distal) sleeve is tubular in shape. A score of 2/3 means that one-third of the sleeve is no longer tubular. A score of 1/3 means that two-thirds of the sleeve are no longer tubular. Finally a score of 0/3 means the entire sleeve is no longer tubular. Re-tightening will occur for patients with a score of 0, 1 or 2.

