The retightening procedure will be performed in a similar fashion as the initial ESG with similar technique, peri-procedural care, transitional diet, and aftercare. However, the retightening procedure will only target open (non-restrictive) portions of the ESG; it should thus be an abbreviated procedure. The number of sutures used in the retightening procedure will be determined by the PI with the goal of re-capturing the tubular configuration of the sleeve.

All patients will continue follow-up with a modified lifestyle intervention program administered over 6 visits in the second year. Laboratory testing will be obtained as detailed in the study schedule of events (Appendix F).

Participants randomized to the ESG group will follow the same follow-up schedule as control participants in Level 1. Participants will receive \$100 for every 4 visits they attend consecutively in Level 1 with the ability to earn a maximum of \$300 at the end of the first 12 months of Level 1. In Level 2, participants will report for 6 visits, with the potential to earn \$100 for every 2 consecutive visits they attend. If they attend all 6 visits, they will receive a bonus of \$300 at the final visit, for a potential total earned of \$900 for all visits across two years.

Participants will return for follow-up visits per the schedules of events below (Appendix F). An in-window visit will be considered as reporting for follow-up visits within a two-week window of the visit date.

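### Section 4.2.1 would declare re-tightening efficacious from an uncontrolled 50% proportion, and sections 4.1 and 5.5.1.1.2 disagree on who has the repeat endoscopy that supplies the durability denominator

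*Combined protocol and SAP*

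**What the plan says.** Objective 4 in section 3 is to "Assess the impact of re-tightening the ESG on weight loss trajectory". Section 4.2.1 turns this into a success rule: re-tightening is efficacious if at least 50% "of the cohort undergoing the re-tightening maintaining or losing weight compared to the re-tightening weight at 12 months after the re-tightening procedure". No control group, reference rate, interval or test accompanies the rule there or in section 7. Section 4.1 describes Level 2 as "the crossover, non-randomized study phase with outcomes for a) the initial treatment group at 24 months post ESG".

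Section 5.5.1.1.2 determines who is re-tightened. ESG patients above 25% EWL have no second endoscopy. Those who "have not achieved >25% EWL at the end of Level 1 will undergo a repeat upper endoscopy at 52 to 60 weeks" are scored from 0 to 3, and "Re-tightening will occur for patients with a score of 0, 1 or 2". The procedure is repeated "with similar technique, peri-procedural care, transitional diet, and aftercare", and a six-visit lifestyle programme continues through year 2.

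Section 4.2.1 also sets a durability rule: "greater than 70% of the cohort undergoing repeat endoscopy achieving a score of" at least 1 out of 3. For the group having that endoscopy, section 4.1 says: "Those who had the ESG will undergo a repeat upper endoscopy at 52 weeks +- 4 weeks to evaluate the durability of the plications". This carries no EWL condition and spans weeks 48 to 56. Table 2 agrees with section 5.5.1.1.2 on timing: re-tightening falls in weeks 52 to 60, for those who qualify.

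**The concern.** The 50% rule attaches the word *efficacy* to a before-and-after proportion. At least four things could keep weight level or lower over that year: the re-tightening, the repeated transitional diet (four weeks of liquids and two of soft food), continued lifestyle visits, and the selection of patients whose 12-month result was poor. The rule cannot separate them. If it is met, the trial would report an efficacy finding against objective 4 that the data cannot support.

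The second problem is one of definition. The durability proportion is taken over patients who have the repeat endoscopy, and two sections define that group differently. A reader could take the result as describing all ESG patients when, under section 5.5.1.1.2, it describes only those not above 25% EWL. Sites also have two instructions on whom to re-endoscope and when.

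**Working it through.** **Planning inputs.** The plan gives no sample size or error rate for either rule, so there is no figure for them to reproduce. The inputs borrowed below are the ESG-arm mean of 25% EWL and SD of 30% in section 7.1, and these do reproduce that section's own power statement. With 34 and 51 patients, SE = √(30²/34 + 5²/51) = √(26.47 + 0.49) = 5.19, and 15/5.19 = 2.89. A two-sample t-test with unequal variances then has 80.1% power, against the stated 80%. With 45 and 68 patients it has 90.2%, against the stated 90%.

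**Number re-endoscoped.** Under section 5.5.1.1.2 at the planning mean, with a normal distribution assumed, P(EWL ≤ 25) = Φ((25 − 25)/30) = 0.5, so 80 × 0.5 = 40. This ignores dropout and is an upper bound on the number re-tightened, because a score of 3 is not re-tightened. Under section 4.1 the number is up to 80. A better mean result than 25% would make the re-tightened group smaller and the interval below wider.

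**Precision of a pass.** 20/40 = 50% meets the rule. Its exact (Clopper-Pearson) 95% CI is 33.8% to 66.2%.

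**Can the rule be met with no effect?** For a given patient, height and baseline weight are fixed, so weighing no more at the later visit is the same as %EWL not falling. Let 12- and 24-month %EWL be bivariate normal with SD 30 and correlation ρ, select EWL ≤ 25 from a mean of 25, and let re-tightening do nothing. Let k be the average regain in EWL points. Then

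P(not gaining | selected) = 2 ∫₋∞⁰ Φ{[(ρ − 1)z − k/30] / √(1 − ρ²)} φ(z) dz,

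which for k = 0 reduces to 1/2 + arcsin(√((1 − ρ)/2))/π.

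| Assumed average regain k | ρ = 0.95 | ρ = 0.5 |
|---|---|---|
| 0 points | 55% | 67% |
| 5 points | 34% | 60% |
| 10 points | 17% | 53% |

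Both ρ and k are assumptions; the documents give neither. Selection on the sleeve score is not modelled. The table shows that a procedure with no effect may pass or fail, depending on quantities the rule does not control.

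**Endoscopy group, side by side.**

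| | Section 4.1 | Section 5.5.1.1.2 |
|---|---|---|
| Who | All who had ESG | Only those not above 25% EWL |
| When | Weeks 48 to 56 | Weeks 52 to 60 |
| Number at the planning mean | Up to 80 | About 40 |
| Smallest count above 70% | 57/80 (71.3%) | 29/40 (72.5%) |

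**Follow-up time.** The last scheduled weight in Table 2 is week 104. Re-tightening at weeks 52 to 60 leaves 104 − 60 = 44 to 104 − 52 = 52 weeks, before the two-week visit window.

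**The case against.** The best defence is that section 4.2.1 states an operational benchmark and not an inference. No hypothesis or alpha is attached to it, Level 2 is openly non-randomized, and this is one secondary endpoint among many. Section 7.2.2 plans a regression of 12-to-24-month EWL change on plication durability and number of sutures. It adjusts for first-year %EWL, which partly addresses the selection of low responders, and it is labelled observational. The durability denominator is named where the endpoint is defined, section 5.5.1.1.2 says who is in it, and the outlier is one sentence in a general description.

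Most of this is fair and limits the weight of the point. It does not remove it. The observational label belongs to the regression and does not reach the 50% rule, which still yields a declaration of efficacy. The sentence in section 4.1 is current text and contradicts the operative section.

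Four stronger readings are tempting, and the documents do not support them:

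- *The primary comparison is contaminated, because the section 4.1 window opens at week 48.* Section 5.5.1.1.2 places the repeat endoscopy after the end-of-Level-1 %EWL assessment, and Table 2 starts re-tightening at week 52.
- *The durability rule contradicts itself, because scores 1 and 2 count as durable yet are re-tightened.* Partial persistence and a trigger for repair are different questions, and both thresholds are stated. Showing the score distribution is a reporting preference.
- *The 50% rule has a known false-positive rate, or is bound to pass.* The documents give no expected not-gaining rate, so no error rate can be stated.
- *The restricted denominator biases durability in a known direction.* No document relates sleeve score to EWL, so neither the direction nor the size can be given.

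**Conclusion.** The point holds in two parts. First, meeting the 50% rule cannot be attributed to re-tightening and could occur with no effect. Lack of attribution follows from the design alone and rests on no assumption. The 55% to 67% illustration rests on normality, the planning mean and SD, no average regain and the assumed correlations. A bare pass would carry an interval of about 34% to 66% at best, since 40 is an upper bound at the planning mean. Second, the repeat-endoscopy group is defined in two incompatible ways, so the durability rule applies to about 40 or up to 80 patients, and the timing differs as well.

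Neither part shows that re-tightening is ineffective or that sleeves do not last. The consequence is limited to secondary endpoints in the non-randomized phase, and the randomized 12-month comparison stands. The plan should be corrected, because following it as written could yield an efficacy statement the data cannot carry and a durability figure with an ambiguous population.

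**What to change.** 1. In section 4.2.1, replace the efficacy declaration with a descriptive proportion of re-tightened patients not above their re-tightening weight at week 104, with an exact 95% confidence interval. State that this is 44 to 52 weeks after re-tightening, before visit windows. Extend the observational label of section 7.2.2 to it.
2. Align section 4.1 with section 5.5.1.1.2 and Table 2: repeat endoscopy at weeks 52 to 60, after the week-52 weight, only for ESG patients not above 25% EWL.
3. State beside the 70% rule that the durability proportion applies only to re-endoscoped patients not above 25% EWL. Showing the full 0-to-3 score distribution next to it is optional.

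The cost is wording in two sections and one interval, with no new visits, procedures or patients. The price is a weaker claim for one secondary endpoint and a durability statement limited to a selected group. The change does not make the re-tightening result causal; that would need a comparator, which this design does not have.

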4.6 Exclusion Criteria

1. History of foregut or gastrointestinal (GI) surgery (except uncomplicated cholecystectomy or appendectomy)
2. Prior gastrointestinal surgery with sequelae, i.e. obstruction, and/or adhesive peritonitis or known abdominal adhesions.
3. Prior open or laparoscopic bariatric surgery.
4. Prior surgery of any kind on the esophagus, stomach or any type of hiatal hernia surgery.
5. Any inflammatory disease of the gastrointestinal tract including severe (LA Grade C or D) esophagitis, Barrett's esophagus, gastric ulceration, duodenal ulceration, cancer or specific inflammation such as Crohn's disease.
6. Potential upper gastrointestinal bleeding conditions such as esophageal or gastric varices, congenital or acquired intestinal telangiectasis, or other congenital anomalies of the gastrointestinal tract such as atresias or stenoses.
7. Gastrointestinal stromal tumors, history of premalignant gastric lesions (intestinal metaplasia), history of familial and non-familial adenomatous syndromes.
8. A gastric mass or gastric polyps > 1 cm in size.
9. A hiatal hernia > 4cm of axial displacement of the z-line above the diaphragm or severe or intractable gastro-esophageal reflux symptoms.
10. A structural abnormality in the esophagus or pharynx such as a stricture or diverticulum that could impede passage of the endoscope.
11. Achalasia or any other severe esophageal motility disorder
12. Severe coagulopathy.
13. Insulin-dependent diabetes (either Type 1 or Type 2) or a significant likelihood of requiring insulin treatment in the following 12 months or a HgbA1C \geq 9.
14. Subjects with any serious health condition unrelated to their weight that would increase the risk of endoscopy
15. Chronic abdominal pain
16. Motility disorders of the GI tract such as gross esophageal motility disorders, gastroparesis or intractable constipation
17. Hepatic insufficiency or cirrhosis
18. Use of an intragastric device prior to this study due to the increased thickness of the stomach wall preventing effective suturing.
19. Active psychological issues preventing participation in a life-style modification program as determined by a psychologist
20. Patients unwilling to participate in an established medically-supervised diet and behavior modification program, with routine medical follow-up.

21. Patients receiving daily prescribed treatment with high dose aspirin (> 80mg daily), anti-inflammatory agents, anticoagulants or other gastric irritants.

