5.4 Randomization

Participants will be stratified to three groups (Obesity, Obesity HTN, and Obesity DM) and will be randomly assigned to treatment or control group with a 1:1.5 allocation per a computer generated randomization using variable block randomization.

Participants will be notified of their randomization assignment on the day of the randomization visit. Participants randomized to the control group will proceed to an appointment with the dietitian for their Week 1 visit on the day of randomization. Participants randomized to the treatment group will proceed to a brief visit with the dietitian to review the post-op liquid diet, and the ESG will be scheduled within 30 days of randomization. Participants of child-bearing potential will be required to have a pregnancy test within 7 days of the scheduled ESG.

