Patients will be prescribed the following medications after the procedure to manage expected post-procedural symptoms:

- Zofran 4mg rapid dissolving pills taken every 6 hours as needed for nausea for 7 days
- Phenergan 25mg suppositories taken twice daily as needed for nausea for 7 days
- Low dose liquid narcotic taken every 6 hours as needed for pain for 5 days
- Omeprazole 40mg capsule to be opened in apple sauce for the first 7 days after ESG, then taken as whole capsule daily for 12 months from date of ESG
- Ativan 0.5 mg taken orally once daily for up to 3 days as needed for intractable nausea or anxiety.

Admission for a 23 hours observation for symptom management is optional but permissible. All ESG patients will be given instructions prior to being discharged from the facility to help manage post-procedural symptoms, including nausea, vomiting and/or abdominal pain. Study staff will call patients once between 18-36 hours after the procedure to assess symptoms and to relay any issues to the PI. If the PI feels it is necessary to see a patient in clinic, an unscheduled visit will be scheduled appropriately.

All patients undergoing ESG will go on a 6 weeks transitional diet consisting of 4 weeks of full liquid protein shakes and 2 weeks of soft pureed diet (Appendix G). The transitional diet is designed to allow suture healing and incorporation within the plicated gastric wall. After the transitional diet period, all patients will be on a low-calorie healthy diet personalized by the dietician according to individual patients' needs and conducive to weight loss. Physical activity, including 150 minutes of aerobic exercise per week, will be encouraged and assessed for compliance during the study. It may be recommended for patients to take two chewable multivitamins and one calcium plus vitamin D supplement daily starting within 1 week of the ESG.

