TABLE 2. MERIT SCHEDULE OF EVENTS (Year 2, Level 2, Treatment Group, 80 Patients)							
	ESG retightening [†]	Post-Op Clinical Eval ^{**}	Follow-up after ESG retightening OR Week 60 [†]	Week 72-76*	Weeks 80, 88, 96	Week 104 (Final Year 2 visit)	Unscheduled Visit
Visit Number	17	-	18	19	20, 21, 22	23	
Informed consent							
Complete Physical Exam (CPE) by Investigator or Investigator delegated / medically qualified team member				X		X	X
Investigator or Investigator delegated/medically qualified team member exam			X	X	X	X	X
EKG if (> 50 yo)							
Formal nutritional assessment							
Formal psychology evaluation							
Pregnancy test (females of childbearing potential only)							
Laboratory tests ^{**}				X		X	
Questionnaires [#]				X		X	
Inclusion/exclusion criteria							
Endoscopy / Procedure	X						
Procedure Assessment Form	X						
GERD Questionnaire + Activity Assessment Form			X	X	X	X	
Weight, BMI/height, Waist and Hip Circumference Form	X		X	X	X	X	X
Vital Signs Form	X		X	X	X	X	X
Adverse Events Form		X	X	X	X	X	X
Medications Form ^{##}			X	X	X	X	X
Post-enrollment Nutrition / Exercise / satiety counseling and assessment			X	X	X	X	
Subject Satisfaction Questionnaire (study termination)						X	

** Electrolytes, Creatinine, CBC, Iron, TIBC, B12, 25-hydroxy Vitamin D, TSH, HgA1c, fasting blood sugar and insulin, PTT, fasting lipids profile (total cholesterol, LDL, HDL, and Triglyceride), ALT, AST, ALK-P, total bilirubin, direct bilirubin, BUN, total protein, albumin, CRP, urinalysis; also include PYY-1, GLP-1 and total Ghrelin pending sites' availability to analyze

IWFQOL-Lite, SF36, PHQ9, Pittsburg Sleep Quality Index (PSQI), Three factor eating questionnaire (TFEQ)

Record all medications including dose and frequency; especially diabetes and blood pressure medication.

++ Post-op phone call, no clinic visit, to occur between 18-36 hours post-op

+ ESG retightening to occur between Weeks 52-60 for those who qualify with in-clinic follow-up visit to occur 4 weeks post retightening, or subjects to continue to Week 60 for those who do not qualify for ESG retightening

*Lab draw to occur between Week 72-76

5.6.1.1.3 Schedule of Events for Control Group, Crossover in Year 1, Level 1

TABLE 3. MERIT SCHEDULE OF EVENTS (Year 1, Level 1, Control Group, 120 patients)									

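### The esophagitis 'incidence' endpoint is, as written, a prevalence at one endoscopy: it uses no pre-ESG baseline and takes no account of omeprazole status at the reading

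*Combined protocol and SAP*

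**What the plan says.** The endpoint in section 4.2.1 is "Incidence of esophagitis at repeat endoscopy at 12 months (level 1"), with LA grading on a form in an appendix. Section 7.2.2 groups it with the binary outcomes to be compared between arms by an unadjusted Pearson chi-square test.

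Four other places bear on it.

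- **Entry.** Section 4.6 excludes "Any inflammatory disease of the gastrointestinal tract including severe (LA Grade C or D) esophagitis". Grades A and B are not named.
- **Index endoscopy.** Section 5.5.1.1.2 has an upper endoscopy immediately before ESG. Its stated purpose is to check for contraindications.
- **Omeprazole.** The same section prescribes it after ESG, first as an opened capsule, "then taken as whole capsule daily for 12 months from date of ESG".
- **Repeat endoscopy.** Section 4.1 states "Those who had the ESG will undergo a repeat upper endoscopy at 52 weeks +- 4 weeks". Section 5.5.1.1.2 instead says that ESG patients not above 25% EWL "will undergo a repeat upper endoscopy at 52 to 60 weeks to assess the durability of the plications", and that those above 25% EWL have none. Table 2 in section 5.6 agrees with the later window: "ESG retightening to occur between Weeks 52-60 for those who qualify".

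**The concern.** Incidence means new cases among people who did not have the condition at the start. The plan's wording counts everyone with esophagitis at the repeat endoscopy, over everyone examined. A patient with grade A disease on the day of ESG who still has it a year later would be reported as an incident case.

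The second issue is the state in which the reading is taken. Some patients may be examined within the prescribed omeprazole course and others after it, and nothing in 4.2.1 or 7.2.2 records or reports which. If acid suppression affects what the endoscopist sees, the pooled figure mixes two conditions.

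What is at stake is a tolerability figure. A reader would take a published esophagitis incidence after ESG as the rate of new disease, and the plan as written does not produce that.

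**Working it through.** The documents give no esophagitis rate, sample size or power, so there is no plan figure to reproduce.

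**1. What is counted.** Let b be the proportion with grade A/B disease at the pre-ESG endoscopy, p the proportion of those who still have esophagitis at the repeat endoscopy, and i the proportion newly affected among those free of it at index.

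Reported proportion = b·p + (1 − b)·i

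Difference from true incidence = b·(p − i)

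The two agree only if b = 0 or p = i. None of b, p or i is in the documents. Purely to show the mechanism, assume i = 10%:

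| b (assumed) | p = 100% (assumed) | p = 50% (assumed) |
|---|---|---|
| 5% | 14.5% | 12% |
| 10% | 19% | 14% |
| 20% | 28% | 18% |

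These are not estimates for this trial.

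**2. When the reading falls.** Inputs: the omeprazole course ends 12 months (taken as 52 weeks) after ESG; the window is 48–56 weeks (section 4.1) or 52–60 weeks (section 5.5.1.1.2 and Table 2). The text does not say whether those weeks run from ESG or from randomization. Section 5.4 says "the ESG will be scheduled within 30 days of randomization", a delay of up to 30/7 = 4.3 weeks.

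Weeks from end of course = endoscopy week − (delay + 52)

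| Clock | Window 48–56 | Window 52–60 |
|---|---|---|
| From ESG (delay 0) | −4 to +4 | 0 to +8 |
| From randomization, ESG 30 days later | −8.3 to −0.3 | −4.3 to +3.7 |

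On the ESG clock the two windows together span 4 weeks before to 8 weeks after the prescribed course ends. The 8-week maximum needs the later window and no delay.

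**3. Whether drug status is recorded at the reading.** In Table 2 the Medications Form is not marked in the retightening column, where the endoscopy takes place, although the weight and vital signs forms are. In Table 1 the Medications Form is marked at the index ESG. The nearest scheduled medication records are week 52 and the next follow-up visit (4 weeks after retightening, or week 60).

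**4. Who has a reading.** If only ESG patients not above 25% EWL are endoscoped, the section 7.1 assumption (mean 25, SD 30), taken as normal, gives P(EWL ≤ 25) = Φ((25 − 25)/30) = 0.50, so 0.50 × 80 = 40 patients before dropout. The year-1 control schedule (Table 3) marks no endoscopy. Crossover controls have one before their own ESG, but they are a selected subset, examined before any protocol omeprazole. The chi-square in 7.2.2 therefore has no matching control reading.

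**The case against.** The strongest reply is that this is mostly a matter of wording. A pre-ESG endoscopy is done, Table 1 has a Procedure Assessment Form at that visit, and the LA form sits in an appendix that is not in the available text, so the index grade may well be collected. That stands: a reader might infer that the index grade goes unrecorded, and the documents do not support that. What can be said is that the endpoint and analysis text do not use it.

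The exclusion criterion opens by barring any inflammatory disease of the GI tract, which could be read to cover grades A and B. That is possible, but specifying severe disease as grade C or D would then serve little purpose, so admission of A and B remains the natural reading.

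On omeprazole, the text gives a length of prescription, not actual use. It does not say that patients stop at 12 months. That the drug alters the grade found is general clinical knowledge, and its size cannot be taken from these documents. This is why the drug-status point is secondary. A reader might also want an average time off drug at the reading, but that depends on the clock and on how examinations spread over the window, neither of which is stated. An average delay of 15 days would by itself move it by about 2.1 weeks (15/7).

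Finally, this is one secondary endpoint with no power claim, and two larger limits on it remain whatever the definition: the endoscoped group may be selected on weight loss, and controls have no matching reading. That is correct, and it shapes the fix.

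**Conclusion.** The point holds as one of definition. As written, the endpoint is a point prevalence carrying the name incidence, because grade A/B disease can enter and no baseline is subtracted. The reading may also fall before or after the end of the prescribed omeprazole course, with no medication record scheduled at that visit in Table 2 as it appears in the text.

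The size of either effect cannot be derived from the documents. The conclusion rests on the natural reading of the exclusion criterion and on the absence of any baseline in 4.2.1 and 7.2.2.

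Two stronger readings are tempting and unsupported. One is that the reported figure will be too high by some stated number of points: that needs an assumed prevalence and full persistence of disease through a year of prescribed omeprazole, and lower persistence shrinks it markedly. The other is that a better definition would show how often ESG causes esophagitis: without a control reading, and with endoscopy possibly confined to patients not above 25% EWL, it would not.

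**What to change.** In sections 4.2.1 and 7.2.2:

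- Define the outcome as new or worsened LA grade at the repeat endoscopy relative to the pre-ESG endoscopy, among patients with both readings.
- Reserve the word incidence for new cases, with patients free of esophagitis at the pre-ESG endoscopy as the denominator. Report total prevalence alongside.
- Record omeprazole status at the repeat endoscopy (taking, or days since last dose) and report it descriptively with the rate. Formal strata would be too sparse in about 40 patients.
- Present the result as a descriptive within-ESG figure for the patients actually endoscoped, and remove it from the between-arm chi-square.
- Reconcile section 4.1 with section 5.5.1.1.2 and Table 2 on who is endoscoped and when, and state whether the weeks count from ESG or from randomization.

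The cost is analysis-plan wording, one medication entry at a visit already scheduled, and confirmation that the LA grade is captured at an endoscopy already performed. The downside is small numbers: the index-free denominator will be no larger than the endoscoped group, and any rate should carry a confidence interval. No change to treatment or to endoscopy timing is proposed.
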